3.2 Investigational Product (treatment, device) and Indication

The Aspen whirlpool from NetSpa is an inflatable pool with four seats and a capacity of 700 litres. The heating of the 168cm x 168cm hot tub can be adjusted up to 42°C. The water filtration runs automatically. The CE marking indicates that the product fulfils the essential requirements of the European Directives 2006/95/ EC (Low Voltage): 2004/108/ EC (electromagnetic compatibility) 2011/ 65 EU (restriction of the use of certain substances in equipment e) 2009/125/EC (Ecodesign of Energy-Related Products).

Image of the Aspen whirlpool: <https://www.netspa.eu/en/produit/2020-spa-netspa-aspen>

Simulated altitude training is rapidly becoming the most promising development in the world in terms of athletic performance and peak fitness. With the Cloud 9, a simulated altitude of up to 4000 m above sea

SUPSI

level can be achieved. This corresponds to an oxygen partial pressure of 12.7 %. The Cloud 9 altitude training device is designed for all levels of athletes (including amateurs) who want to improve their performance. The Cloud 9 is a solid, certified product that complies with the European Directives on electromagnetic compatibility, machinery directive, air pressure equipment and low voltage equipment (89/336/EEC, 91/368/CEE, 93/68/CEE, 97/23/EC, EN61010-1).

Image of the Cloud 9: <https://chasingtargets.eu/altitude-tent-rental-service/>

An already approved ethics application with Cloud9 has already been carried out by the research staff in the laboratory premises in Landquart (BASEC ID 2019-00504). The research staff also have experience in the field of cold water baths based on an already approved ethics application, which investigated the effect of cold water baths following to a muscle damage protocol (BASEC ID PB_2016-01125).

All those present are able to carry out "first aid" measures. A fully functional and annually serviced defibrillator is located in the research laboratory and can be put into operation by all investigators present. The room in which the study takes place has the following dimensions: 7m x 14m x 2.5m (98 square meters or 245 cubic meters) and can be ventilated.

3.3 Preclinical Evidence

Various studies have already shown that cooling has a positive influence on performance and recovery capacity compared to non-cooling measures. These positive effects have been demonstrated both on a subjective level (Ascenso, 2011; Bailey, 2007; Minett, 2012; Ingram, 2009; Delestrat, 2013; Elias, 2012), as well as on an objective level (Tseng, 2013; Pournot, 2011; Ascenso, 2011; Pointon, 2011; Tucker, 2012, Heyman, 2009). On the other hand, there are studies that question the effectiveness of cooling in terms of its effectiveness (Leal, 2011; Hassan, 2011; Jakeman, 2011).

To date, only a few studies have investigated the effect of hot water immersion on recovery (Bieuzen 2013, Kuligowski 1998, Pournot 2010, Vaille 2007, Viitasalo 1995). In one study, isometric force recovery

SUPSI

was found to be more effective after the hot water bath compared to other thermotherapies such as a cold water bath and a passive control intervention (Vaile, 2007). Pournot (2010) also found significant changes in subjective symptom assessment, the number of leukocytes and creatine kinase. Cold water baths are already used in the scientific literature for a duration of 10 minutes at a water temperature of 10°C (Hohenauer et al 2018, Hohenauer et al 2020). However, cold water baths have also been carried out for up to 20 minutes at a water temperature of 10°C (Kositsky et al 2020). In the field of hot water baths, studies have already been carried out using water temperatures of 40°C for a duration of 40 minutes (McIntyre et al 2021, Zurawlew et al 2015). No side effects were reported with these water baths. Repeated cold and hot water interventions after 2 hours could help to reduce the intracellular volume increase that occurs within this period (White et al 2013) after exercise.

Studies under hypoxic conditions have already been conducted in the medical field with a wide variety of pathologies, such as obesity under stress (Girard, Malatesta, and Millet 2017, Park et al. 2019) and also with senior citizens (Pramsohler et al. 2017). In addition to physiological changes, hypoxic conditions can lead to psychological changes (Taylor et al. 2015). Chronic altitude exposure can further lead to physiological changes (Smith et al. 2014)

It is known that cognitive and physical performance in normoxia improves with light moderate exercise (Chang et al. 2012). In addition, there is growing evidence that exercise can even reverse the negative effects of hypoxia on cognitive performance (Ando et al. 2013, Komiyama et al. 2017).

3.4 Clinical Evidence to Date

Current research results regarding the effects of thermotherapy and training under hypoxia conditions are listed in chapter 3.3.

According to the authors' knowledge, there are currently hardly any clinical studies that contrast the psychophysiological effects of thermotherapy with simulated altitude training and investigate its recovery.

3.5 Dose Rationale / Medical Device: Rationale for the intended purpose in study (pre-market MD)

Doctors and physiotherapists can opt for cold treatments in their treatment, for example, to relieve pain. However, these professional groups not only work with patients but also with amateur and elite athletes and also provide them with individualised care. The project uses the Aspen hot tub from NetSpa. This is used within the scope of the intended application and in accordance with the operating manual. The applied temperatures do not pose a risk to the test subject at any time. The safety instructions are strictly followed.

The temperature for hot water immersion of 40°C is generated for a maximum of 10 minutes (and again after 2 hours). With this setting, we are within the manufacturer's recommendations from the operating manual. For cold water immersion, a temperature of 10°C is chosen for 10 minutes (and again after 2 hours). Physiotherapists, sports physicians and coaches can benefit from these findings. The question of whether the recovery phase can be shortened or whether performance can be increased by means of cooling applications is legitimate. These two parameters include not only objective values but also subjective information from the athlete.

During the normobaric, hypoxic situation, an altitude of up to 4000 m.a.s.l. is simulated, which corresponds to an oxygen partial pressure of 12.7%. This situation is realized with the help of Cloud 9.

SUPSI

3.6 Explanation for choice of comparator (or placebo)

In order to produce a high-quality study, the test subjects are each assigned to an experimental group, which are later compared with each other. The assignment is carried out randomly. Randomization is guaranteed by drawing a lot.

Cold water bath vs. hot water bath vs. hypoxia group vs. passive control group

Four groups are compared to each other in order to compare the effect of cold water immersion versus hot water immersion, as well as the hypoxia group and the passive control group. The aim is to analyse the efficiency of thermotherapy on the ability to recover. All groups undergo the jump protocol. Both water bath groups are then immersed up to the sternum in water at a temperature of 10°C or 40°C (1 x 10 min and after 2 hours). The hypoxia group will perform the jumping protocol under hypoxic conditions and will then recover for 10 minutes at room temperature in a supine position like the passive control group.

3.7 Risks / Benefits

For the test subjects, there is a minimal risk of overloading during the maximum jumping exercise (5 x 20) of the ventral thigh muscles until exhaustion. The test subjects are expressly informed that they can stop the maximum load at any time. Furthermore, two examiners will be next to the test subject during the 1 min jumping exercise in order to be able to catch her in case of circulatory problems. A fully equipped emergency kit is in the examination room at all times during the examinations. In the event of circulatory problems due to hypoglycaemia, dextrose, chocolate, and Coca-Cola® Ltd. are also available in the examination room. The test subjects are also advised to complete the test well nourished in order to minimise the risk of hypoglycaemia. A fully functional defibrillator (Lifepak Express Defibrillator, reaplus.ch) which is accessible at all times, is available at our institution. This information is communicated to the test persons (subject information).

During body cooling or heating, there is only a minimal risk for the test subjects due to the short application times. The test subjects enter the water baths in swimwear and without body jewellery (piercings, rings, necklaces, etc.). Furthermore, the test subjects should not apply skin creams or other cosmetics to the skin. The investigators of this study are able to operate a fully functional annually maintained defibrillator. An examiner is at eye level with the test subject during the entire application period and monitors her. The investigators in this study can competently perform "first aid" measures. A "first aid" kit is in the research laboratory at all times. Furthermore, any injury to the musculoskeletal system was defined as an exclusion criterion in order not to provoke a relapse of a past injury.

Possible risks in the situation of hypoxic conditions are the occurrence of headaches, loss of consciousness, disorientation and nausea. Potentially at-risk subjects are identified by the screening procedure and the health questionnaire and are not included in the study. However, the risk is to be classified as low, as studies have already been conducted with obese patients and seniors under hypoxic conditions, which did not lead to any complications.

More information on securing the test subjects can be found in chap. 8.1.1.

The test subjects do not gain any direct benefits from participating in the study.

3.8 Justification of choice of study population

This remaining category A clinical trial (Chapter 4) will be conducted with healthy young female volunteers. The risk of injury is considered low in this test population.

SUPSI

Inclusion criteria

- Young healthy women aged 18 - 35 years
- No surgical interventions on the musculoskeletal system in the trunk area and on the lower extremities
- Anticonceptives

Exclusion criteria

- Current injuries of any kind affecting the trunk and/ or lower extremities
- Injuries to the trunk and/ or lower extremities that occurred less than 1 year ago
- Injuries to the trunk and/ or lower extremities that occurred more than 1 year ago and are still causing symptoms
- Fear of cold and/or hot water intervention
- Fear of hypoxia
- Taking medication of any kind (including self-purchased medication)
- Pacemakers & cardiac arrhythmias
- Known circulatory problems
- Positive pregnancy test
- Diagnosed skeletal static deviations
- Appendectomy less than 2 years ago
- Raynaud's syndrome

Before agreeing to participate in the study, the test subjects are given comprehensive information about the procedure and possible risks. They will also receive the information in written form and have the opportunity to ask questions. The informed consent form explains to them what their rights and obligations are if they participate. The subject information states that female subjects agree to take a pregnancy test (urine test) if they have decided to participate in the study. This test will be carried out once the test subjects have signed the consent form. The urine test will be given, received and interpreted by the study director. The test subjects do not have to expect any costs for this test. A positive urine test will result in the exclusion of this study. Only the principal investigator knows the result of the urine tests of the female subjects. Nobody except the head of the research laboratories (study director), the study supervisor, as well as authorised persons of the CEC can view this test result (see point: 2.8. Confidentiality and privacy). In addition, all test subjects are informed that they may withdraw from participation at any time without giving reasons, without any disadvantages for them. The current regulations of the Canton of Graubünden and those of the FOPH for protection against the coronavirus will be taken into account and implemented when conducting the study.

SUPSI

4. STUDY OBJECTIVES

4.1 Overall Objective

In this study, the effect of body cooling for a maximum of 10 minutes and renewed cooling or warming after 2 hours on the subjective muscle soreness and general exhaustion data as well as the objectively measurable MVIC of the ventral thigh muscles and the maximum vertical jump height after exhausting physical exertion will be investigated. In addition to the parameters already mentioned, the heart rate, skin temperature, core body temperature, muscle swelling and oxygen saturation of the thigh muscles as well as inflammation parameters of the blood are to be determined. The effects of thermal application will be contrasted with a hypoxia group and a passive control group and compared directly, 24 hours, 48 hours and 72 hours after the interventions. The aim is to substantiate the state of scientific knowledge and to provide therapists and physicians with further insights. This study can benefit all those who work with amateur and elite athletes.

4.2 Primary Objective

In this project, the effect of post-activity cooling or warming on physiological and psychological recovery parameters is measured and compared to the hypoxia intervention and the passive control group.

Physiological measurements

- Jump height measurement (cm)
- Maximum voluntary isometric thigh contraction (kg)
- Muscle swelling (mm)
- Blood oxygen saturation (%)
- Oxygen saturation of the muscles (%)
- Heart rate (bpm)
- Skin temperature (°C)
- Core Body Temperature (°C)
- Inflammation parameters; IL6 (pg/ml), CRP (mg/dl), creatine kinase (U/L)

Psychological measurements

- Dyspnea questionnaire (mod. Borg scale)
- Exhaustion questionnaire (Borg scale)
- Subjective muscle soreness (VAS scale)
- Thermal comfort and thermal sensation

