Outcome(s):	
Primary outcomes
 
Physiological measurements
 
• Jump height measurement (cm)• Maximum Voluntary Isometric thigh Contraction (kg)• Muscle swelling (mm)• Blood oxygen saturation (%)• Oxygen saturation of the muscles (%)• Heart rate (bpm)• Skin temperature (°C)• Core Body Temperature (°C)• Inflammation parameters: IL6 (pg/ml), CRP (mg/dl), creatine kinase (U/L) 
Psychological measurements
 
• Dyspnea questionnaire (mod. Borg scale)• Exhaustion questionnaire (Borg scale)• Subjective muscle soreness (VAS scale)• Thermal comfort and thermal sensation 
Secondary outcomes: none

Study design:	Randomised, controlled trial

SUPSI

Inclusion / Exclusion criteria:	
Inclusion Criteria
 
• Young, healthy women aged 18 – 35 years• No surgical interventions on the musculoskeletal system in the trunk area and lower extremities• Anticonceptives 
Exclusion criteria
 
• Current injuries of any kind affecting the trunk and/or lower extremities• Injuries to the torso and/or lower extremities that occurred less than one year ago• Injuries to the trunk and/or lower extremities that occurred more than one year ago and are still causing symptoms• Fear of cold and/or hot water intervention• Fear of hypoxia• Taking medication of any kind (even self-purchased)• Pacemakers & cardiac arrhythmias• Known circulatory problems• Positive pregnancy test• Diagnosed skeletal static deviations• Appendectomy less than 2 years ago• Raynaud's syndrome
--	--

SUPSI

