Measurements and procedures:	
Subject recruitment The subject information and consent form are given to the test subjects. Questions may be asked. If the test subject agrees with the information, she will be asked to attend the first contact day. This includes the explanations on site, signing of the consent form, and the completion of the health questionnaire. The pregnancy test must be negative. Once all tests have been passed, an appointment is made for the intervention.
 
Measurement the maximum arbitrary isometric thigh muscle contraction (MVIC) MVIC is performed on the Cor 1 – ergometer chair for biomechanical measurements V1.0 and is expressed in kg (www.otbioelettronica.it). The conduction velocity is measured using the surface electromyogram system EMG-USB2 from OT Bioelettronica (otbioelettronica.it), band-pass filtered between 10-750Hz and rectified (full-wave rectify). MVIC is measured on the Cor 1 ergometer chair in 90° knee flexion. The raw data of muscle activity to measure conduction velocity is processed using OT Bioelettronica's software (MISO II). The electrodes are placed according to the guidelines of Barbero et al. (2012) "Atlas of Muscle Innervation Zones". The measurement takes place directly, 24 hours, 48 hours and 72 hours after the intervention.
 
Jump height measurement The jump height after exercise is determined using a jump height measuring plate designed for this purpose (Just Jump Plate, Probotics Inc., Huntsville, USA). The test subjects assume a standing position on the plate. To measure the jump height, the test subjects are allowed to start from the squatting position (squat jump). The arms must be positioned at the hips during the entire movement. The jump height is measured in cm and takes place, directly, 24 hours, 48 hours and 72 hours after the intervention takes place.
 
Skin temperature The skin temperature is measured using the iButton System (http://www.ibuttonlink.com). The self-adhesive sensors transmit the information about the skin temperature wirelessly to a computer. The skin temperature is measured immediately after the intervention. The iButtons are attached with a strip of tape to the following locations: center of the shoulder blade, neck (6th cervical vertebra), back of the hand, center of the shin, center of the thigh. The iButtons are removed from the affected areas during the cold or hot water bath and then reattached. Skin temperature is also recorded using the FLIR A655 sc series infrared camera (InfrarotTec Systems, Ranstadt, Germany). A total of seven recordings are taken; baseline, before, during, and after the intervention.
 
Core Body Temperature The core body temperature is determined via the e-Celsius® Performance (https://www.bodycap-medical.com). This non-invasive, disposable, ingestible capsule continuously monitors and records core body temperature and transmits the data wirelessly to a monitor (BodyCAP medical, Hérouville Saint-Clair, France). Core body temperature is measured before, during, and after the intervention.

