Study Centre(s):	University of Applied Sciences and Arts Southern Switzerland Physiotherapy Graubünden Rehabilitation Research Laboratory 2rLab Rehabilitation and Exercise Science Group [name]
Statistical Considerations:	
The effectiveness of repeated cold and hot water baths on recovery and performance is tested by:
 
Repeated measures analysis of variance (MANOVA)
 
Factors:
 
• Protocol• Task (repeated cold water immersion vs. repeated hot water immersion, repeated cold water immersion vs. control group, repeated hot water immersion vs. control group, repeated cold water immersion vs. passive group with hypoxia conditions, repeated hot water immersion vs. passive group with hypoxia conditions)• Time (these factors are measured immediately after cooling/warming and 24 hours, 48 hours and 72 hours after the interventions). 
The significance level is set at $P < 0.05$, and the statistical data analysis is performed with SPSS 27.

SUPSI

GCP Statement:	This study will be conducted in compliance with the protocol, the current version of the Declaration of Helsinki, the ICH-GCP or ISO EN 14155 (as far as applicable) as well as all national legal and regulatory requirements.
-----------------------	---

SUPSI

ABBREVIATIONS

AE	Adverse Event
BASEC	Business Administration System for Ethical Committees, (https://submissions.swissethics.ch/en/)
CA	Competent Authority
CEC	Competent Ethics Committee
CK	Creatine Kinase
CRF	Case Report Form
CRP	C-reactive protein
ClinO	Ordinance on Clinical Trials in Human Research (in German: KlinV, in French: OClin, in Italian: OSRUm)
eCRF	Electronic Case Report Form
CTCAE	Common terminology criteria for adverse events
DSUR	Development safety update report
GCP	Good Clinical Practice
IB	Investigator's Brochure
Ho	Null hypothesis
H1	Alternative hypothesis
HRA	Federal Act on Research involving Human Beings (in German: HFG, in French: LRH, in Italian: LRUm)
IL6	Interleukin 6
IMP	Investigational Medicinal Product
IIT	Investigator-initiated Trial
ISO	International Organisation for Standardisation
ITT	Intention to treat
MD	Medical Device
MedDO	Medical Device Ordinance (in German: MepV, in French: ODim)
MVIC	Maximum voluntary isometric muscle contraction
PI	Principal Investigator
SDV	Source Data Verification
SOP	Standard Operating Procedure
SPC	Summary of product characteristics
SS Test	Pregnancy test

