To the knowledge of the authors, however, there are only limited studies investigating physiological parameters of recovery in laboratory conditions. In addition, various patient groups also suffer from lung dysfunction (such as COPD) and are therefore at least partially under hypoxic conditions. With this study, we can contribute to understanding the psychophysiological responses of recovery under hypoxia.

Aim of the study

In this project, the effect of repeated cold water immersions (10 °C for 10 min and again after 2 hours), repeated hot water immersions (40°C for 10 min and again after 2 hours), a hypoxia group (jump protocol under hypoxia and subsequent supine position for 10 min), and a passive control group (lying still in a supine position for 10 min) will be compared. The influence of these interventions and their effects will be investigated after a maximum jump load (5 x 20 jumps). The objective recovery parameters are vertical jump height, MVIC of the ventral thigh muscle, heart rate, muscle swelling, skin and core body temperature, measurement of inflammatory parameters, oxygen saturation of the blood and thigh muscles. Subjective recovery parameters are the local muscle soreness data, the general exhaustion and shortness of breath as well as information on thermal comfort and temperature sensation. The parameters are measured directly and 24, 48 and 72 hours after exercise. The aim is to determine the effects of thermotherapy in order to be able to make recommendations. The current state of scientific knowledge calls for further studies to substantiate or refute effects that have already been established.

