8.2.1 Experimental Intervention

Cold water immersion

Test subjects in this group are asked to take a cold water bath after carrying out the jump protocol. The application lasts 10 minutes (and is repeated after 2 hours) at a water temperature of 10°C. In a sitting position, the water level must reach the sternum.

Hot water immersion

Test subjects in this group are asked to take a hot water bath after carrying out the jump protocol. The application lasts 10 minutes (and is repeated after 2 hours) at a water temperature of 40°C. In a sitting position, the water level must reach the sternum.

In all experimental interventions, an examiner is located directly next to the test person for monitoring at all times.

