H1 Skin temperature is increased by hot water immersion compared to cold water immersion, hypoxia group and passive control group during 72 hours.

Core Body Temperature (°C)

H0 Core body temperature is not increased by hot water immersion compared to cold water immersion, hypoxia group, and passive control group during a 72-hour recovery period.

H1 Core body temperature is increased by hot water immersion compared to cold water immersion, hypoxia group and passive control group during 72 hours.

Inflammation parameters (CRP, IL6, CK)

H0 Inflammation levels are not increased by hot water immersion compared to cold water immersion, hypoxia group, and passive control group during a 72-hour recovery period.

H1 The inflammation rates are increased by hot water immersion compared to cold water immersion, hypoxia group and passive control group during 72 hours.

Subjective information on shortness of breath (mod. BORG)

H0 Subjective information on shortness of breath is not increased by hot water immersion compared to cold water immersion, hypoxia group and passive control group during a 72-hour recovery period.

H1 The subjective information on shortness of breath is increased by hot water immersion compared to cold water immersion, hypoxia group and passive control group during 72 hours.

Subjective data on general exhaustion (BORG)

H0 The subjective data on general fatigue are not increased by the hot water immersion compared to the cold water immersion, hypoxia group and passive control group during a 72-hour recovery period.

H1 The subjective data on general fatigue are increased by the hot water immersion compared to the cold water immersion, hypoxia group and passive control group during 72 hours.

Subjective muscle soreness (VAS)

H0 Subjective muscle soreness is not increased by hot water immersion compared to cold water immersion, hypoxia group, and passive control group during a 72-hour recovery period.

H1 Subjective muscle soreness is increased by hot water immersion compared to cold water immersion, hypoxia group and passive control group during 72 hours.

SUPSI

Thermal comfort and temperature perception

H0 Thermal comfort and temperature perception are not increased by hot water immersion compared to cold water immersion, hypoxia group and passive control group during a 72-hour recovery period.

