H1 Thermal comfort and temperature perception are increased by hot water immersion compared to cold water immersion, hypoxia group and passive control group during 72 hours.

A 2-factor analysis is carried out.

Factor 1: Intervention (cold water immersion vs. hot water immersion vs. hypoxia group vs. Passive Control Intervention)

Factor 2: Time (Baseline, 0, 24 hours, 48 hours, 72 hours)

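### Skin temperature, core temperature and thermal comfort/sensation are ranked as primary recovery outcomes, but skin temperature and sensation mainly show which bath was given, so a significant result on them says little about recovery

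*Combined protocol and SAP*

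**What the plan says.** Section 4.2 gives the primary objective: the "effect of post-activity cooling or warming on physiological and psychological recovery parameters is measured". The comparators are the hypoxia and control groups. The list below it includes skin temperature, core body temperature, and thermal comfort and sensation. Section 3.1 (aim of the study) is explicit: "The objective recovery parameters are vertical jump height, MVIC of the ventral thigh muscle, heart rate, muscle swelling, skin and core body temperature". It then places thermal comfort and temperature sensation among the subjective recovery parameters. The synopsis repeats the list as primary and adds "Secondary outcomes: none".

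Section 11.1 gives each thermal measure its own hypothesis pair, for example "H1 Skin temperature is increased by hot water immersion compared to cold water immersion, hypoxia group and passive control group during 72 hours". The pairs for core temperature and for thermal comfort and perception take the same form. The synopsis introduces the analysis with "The effectiveness of repeated cold and hot water baths on recovery and performance is tested by", followed by a repeated-measures analysis at P < 0.05. In section 11.4.2 the Time factor has the levels baseline, 0, 24, 48 and 72 hours.

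On the exposure, section 8.2.1 says of the cold bath: "The application lasts 10 minutes (and is repeated after 2 hours) at a water temperature of 10°C". The hot bath has the same schedule at 40°C. On timing, the synopsis says "The skin temperature is measured immediately after the intervention", and section 5.1 adds 24, 48 and 72 hours. Sensation is rated from -4 (very cold) to +4 (very hot). Section 5.1 places the rating before and after the intervention. The section 9.1 flow chart places it at baseline and in the bath (or supine) steps, and not at any follow-up.

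Other text points the other way. The synopsis objective names MVIC, jump height, inflammation parameters, swelling, soreness and exhaustion, and no thermal measure. Section 4.1 puts soreness, exhaustion, MVIC and jump height first and brings in the temperatures only as further parameters.

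**The concern.** Skin temperature just after the bath and the hot/cold rating respond to the water whatever happens in the muscle. They show that the assigned bath was delivered. Participants are not blinded, so a woman rating how hot or cold she feels is close to reporting her allocation. For these outcomes the null hypothesis can be truly false for a reason that has nothing to do with recovery, so a smaller significance level is not the remedy.

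As the outcomes are ranked, a significant difference in skin temperature would be a positive result on a primary recovery parameter, equal in standing to one on strength or soreness. A reader of the results could not tell from the outcome list which positive findings bear on the trial's question. Section 3.1 says the trial is meant to support recommendations, so the distinction matters.

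**Working it through.** **Arm sizes.** Section 11.2 needs 33 evaluable women and inflates for 20% loss: 33 × 1.2 = 39.6, rounded to 40, which reproduces the plan's figure. (Division gives 33 / 0.8 = 41.25, so 42.) Section 6.1 gives N = 60. With equal allocation, which is an assumption, the arms hold 33/4 ≈ 8, 40/4 = 10 or 60/4 = 15.

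**Assumptions.** The documents give no SD, correlation or expected temperature shift. I take SD 1.0 or 1.5°C, correlation 0.5 between any two times, and a mean shift at 0 h only: up in the hot arm, down in the cold arm, none in the dry arms and none at 24 to 72 h. For comparison, the water temperatures differ by 40 - 10 = 30°C.

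**Two readings of a positive result for skin temperature.**
1. Group-by-time F test from the 4 × 5 repeated-measures model, P < 0.05, Greenhouse-Geisser corrected (the plan names no correction).
2. The section 11.1 wording: hot above cold, hypoxia and control. This is taken as three t-tests on change from baseline to 0 h, all P < 0.05 in the stated direction.

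Simulated share of positive trials at 8 per arm (SD 1.0 / SD 1.5; ranges are the spread over separate runs):

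| Shift at 0 h, hot / cold | Group-by-time test | Hot above all three arms |
|---|---|---|
| none | 4% / 4% | not tabulated |
| +1 / -1°C | 92% / 48% | 29% / 9-11% |
| +2 / -2°C | 100% / 99.8% | 93% / 56-59% |
| +4 / -10°C | not tabulated | 100% / 99.7% |

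- Larger arms: at ±1°C the group-by-time test rejects in 97% / 62% with 10 per arm and 100% / 87% with 15. At ±2°C it rejects in 100% with either.
- Bonferroni for the 16 listed variables (IL6, CRP, CK, comfort and sensation counted separately), level 0.05/16: at ±2°C it still rejects in 100% / 93% with 8 per arm and 100% / 99% with 10.
- If the hypothesis over 72 hours were read as the group main effect, a ±2°C shift at 0 h only gives 34% / 17% with 8 per arm.

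**Core temperature and sensation.** Neither was simulated. A generic guide is the two-sided t-test of hot against cold at one time, using the noncentral t with 2n - 2 df and noncentrality d√(n/2), where d is the difference in SD units. For d = 2, power is 96%, 98.8% and 99.96% with 8, 10 and 15 per arm. For d = 0.5 to 1, it is only 19 to 56% with 10 per arm. A gap of 2 SD is a modest requirement for hot/cold sensation. For core temperature after a 10-minute bath, nothing in the documents says where d lies. Sensation also does not fit the five-level Time factor, because the flow chart has no rating at the follow-ups.

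**After relabelling.** The synopsis objective leaves eight variables: jump height, MVIC, swelling, IL6, CRP, CK, soreness and exhaustion. With no true effect and independent tests at 0.05, the chance of at least one significant result is 1 - 0.95^8 = 1 - 0.663 = 34%. It is lower if they are positively correlated.

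**The case against.** The strongest defence has four parts.

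First, a reader might infer that the plan would call the baths effective, or recommend them, on skin temperature alone. The documents do not say so. They contain no rule that one significant outcome proves effectiveness. Each alternative hypothesis concerns only its own variable, and several predict that hot water is worse (more swelling, inflammation, soreness and exhaustion). This stands. The fault is that the outcome ranking permits the misreading, not that the plan commits to it.

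Second, the synopsis objective and section 4.1 already put the thermal measures lower. This also stands, but they conflict with the synopsis outcome list and with sections 3.1, 4.2 and 11.1, and nowhere are the measures called checks on delivery.

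Third, every effect size here is assumed. Immersion is to the sternum, while the sensors include the neck and the back of the hand, and no rule says how sites are combined. The shift in the analysed variable is therefore unknown, and the smaller shifts in the table do not give near-certainty.

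Fourth, the protocol describes basic physiological research on bath effects, for which thermal response is a legitimate measurement. That supports keeping the measurements, but not ranking them as primary evidence of recovery.

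**Conclusion.** The point holds. Skin temperature and thermal sensation are ranked as primary recovery outcomes although they mainly reflect the assigned bath, and this conflicts with the protocol's own synopsis objective. A significant primary result without any effect on recovery is likely, depending on the shift: with 8 per arm, about 100% at ±2°C and 48 to 92% at ±1°C for the group-by-time test. For the directional hypothesis it is about 93% or 56 to 59% at ±2°C, 29% or 9 to 11% at ±1°C, and about 100% at +4/-10°C (SD 1.0 or 1.5).

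It would be tempting to say that the trial is all but certain to produce such a result. The documents do not support that: they give no SD or shift and do not name the ANOVA term to be tested, and the directional hypothesis reaches near-certainty throughout the assumed SD range only at the larger assumed shift. Nor do they support treating core temperature as equally clear-cut. It is a bodily response of unstated size and belongs with the other thermal measures only on grounds of role.

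**What to change.** In the synopsis outcome list and sections 4.2, 5.1 and 11.1, move skin temperature, core temperature and thermal comfort/sensation out of the primary recovery outcomes, and align section 3.1. Label them thermal-response (manipulation-check) measures, report them by arm with 95% intervals, and remove their hypothesis pairs from those that test effectiveness. State that effectiveness on recovery is concluded only from the outcomes in the synopsis objective: MVIC, jump height, inflammation parameters, swelling, soreness and exhaustion. Give the role of the remaining listed variables explicitly (blood and muscle oxygen saturation, heart rate, dyspnoea). Blood saturation deserves thought, because it is recorded during a jump protocol that one arm performs under hypoxia.

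Relabelling does not settle multiplicity. The eight remaining variables still need one named primary outcome and time point, or an adjustment.

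The cost is a wording amendment, plus a matching registry change if the registered outcomes are the same, which cannot be checked here. Measurements, visits and participant numbers stay as they are. The sponsor gives up a few primary outcomes that were likely to be significant.
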